### 6.4 MINIMIZATION OF RISKS WITHIN THE STUDY

This study will be monitored to ensure (1) the identification, documentation and analysis of all AEs, and (2) compliance with the protocol, the terms of the participating IEC to protect the safety and rights of all subjects, and federal and local regulations. In addition, risks have been minimized through selection of investigators who are experienced in the surgical procedures included in this protocol.

## 7 SAFETY AND MEDICAL DEVICE VIGILANCE

All adverse events occurring during the study will be recorded on the appropriate case report form page by the investigator. The nature, severity and relation of the adverse event to the study device will be documented.

### 7.1 DEFINITIONS

#### 7.1.1 Adverse Event (AE)

AE is defined as any untoward medical occurrence in a subject. This definition does not imply that there is a relationship between the adverse event and the device under investigation. An AE can therefore be any unintended sign, symptom, disease or injury or any untoward clinical signs (including an abnormal laboratory findings) in subjects, users or other persons whether or not related to the investigational medical device. The following should be reported as AE:

- Untoward medical conditions or signs or symptoms that were absent before starting study treatment.
- Untoward medical conditions or signs or symptoms present before starting study treatment and worsen (increase severity or frequency) after starting study treatment.
- Abnormal laboratory findings.

- Clinical signs or symptoms that require therapy.

### **7.1.2 Adverse Device Effect (ADE)**

ADE is adverse event, related to the use of an investigational medical device. This includes any adverse event resulting from insufficiencies or inadequacies in the instructions for use or the deployment of the device, the operation, or any malfunction of the investigational medical device, device failure or misuse, and any event that is a result of a user error.

### **7.1.3 Serious Adverse Events (SAE)**

A SAE is an adverse event that:

- Led to a death,
- Led to a serious deterioration in the health of the subject that:
  - Resulted in a life-threatening illness or injury
  - Resulted in a permanent impairment of a body structure or a body function
  - Required in-patient hospitalization or prolongation of existing hospitalization
  - Resulted in medical or surgical intervention to prevent permanent impairment to body structure or a body function.
- Led to fetal distress, fetal death or a congenital abnormality or birth defect.

Important medical events that may not result in death, be life-threatening, or require hospitalization may be **serious** when, based upon appropriate medical judgment, they may jeopardize the subject and may require medical or surgical intervention to prevent one of the outcomes listed above.

Inpatient hospitalization or prolongation of existing hospitalization means that hospital inpatient admission and/or prolongation of hospital stay were required for treatment of AE, or that they occurred as a consequence of the event. Hospitalization for elective treatment of a pre-study condition that did not worsen while on study and hospitalizations for treatment of non-adverse events (e.g. cosmetic surgery or diagnostic procedure) are not considered serious adverse events.

Any new SAE that occurs after the study period and is considered to be related (possibly/probably) to the investigational product or study participation should be recorded and reported immediately.

### **7.1.4 Serious Adverse Device Effect (SADE)**

A Serious Adverse Device Effect is an adverse device effect that has resulted in any of the consequences characteristic of a serious adverse event.

### **7.1.5 Unanticipated Serious Adverse Device Effect (USADE)**

USADE is defined as serious adverse device effect which by its nature, incidence, severity or outcome has not been identified in the current version of the risk analysis report or other study related documents.

Note: Anticipated adverse events expected (with relation to the device and/or procedure) are detailed in section 6.2.

## 7.2 ADVERSE EVENTS CLASSIFICATION

AEs reported by the subject or observed by the investigator will be individually listed on an adverse event form in the CRF as follows: the specific event or condition, whether the event was present pre-study, the dates and times of occurrence, duration, severity, relationship to study device, specific countermeasures, and outcome.

Note: Event which was present pre-study is not considered as an adverse event unless it has worsened since the enrollment to the study.

All AEs will be characterized by the following criteria:

- Intensity or Severity
- Relatedness
- Outcome
- Treatment or Action Taken

### 7.2.1 Intensity/Severity Definition

The intensity or severity of the AE will be characterized as follows:

Mild: Transient or mild discomfort; no limitation in activity; no medical intervention/therapy required.

Moderate: Mild to moderate limitation in activity; some assistance may be needed; no or minimal medical intervention/therapy required.

Severe: Marked limitation in activity, some assistance usually required; medical intervention/therapy required, hospitalization possible.

### 7.2.2 Relationship

The investigator will document in his opinion the relationship of the AE to the investigational medical device using the criteria outlined in [Table 1](#).

**Table 1 Adverse Event Relationship Criteria**

Relationship	Criteria
Unrelated	
The subject was not treated by the investigational device.
 
OR
 
The temporal sequence of the AE onset relative to treatment by the investigational device is not reasonable.
 
OR
 
There is another obvious cause of the AE

Unlikely	The relationship with the use of the device seems not relevant and/or the event can be reasonably explained by another cause, but additional information may be obtained.
Possible	The relationship with the use of the investigational device is weak but cannot be ruled out completely. Alternative causes are also possible (e.g. an underlying or concurrent illness/ clinical condition or/and an effect of another device, drug or treatment). Cases where relatedness cannot be assessed or no information has been obtained should also be classified as possible.
Probable	The relationship with the use of the investigational device seems relevant and/or the event cannot reasonably be explained by another cause, but additional information may be obtained.
Related	
There is evidence of exposure to the investigational device.
 
 
• The temporal sequence of the AE onset relative to use with the investigational device is reasonable.
 
• The AE is more likely explained by the investigational device than by another cause.
 
• The AE shows a pattern consistent with previous knowledge of the investigational device.
 

### 7.2.3 Outcome

The clinical outcome of the AE or SAE will be characterized as follows:

**Death** - The SAE CRF must be completed for this outcome

**Recovered** - The patient returned to baseline status

**Ongoing** - Patient did not recover and symptoms continue;

**Recovered with sequelae** - The patient has recovered but with clinical sequelae from the event

**Unknown** - The patient outcome is unknown

### 7.2.4 Treatment or Action taken

The treatment or action taken after the occurrence of an AE or SAE will be reported as:

**Interventional Treatment** - Surgical, percutaneous or other procedure

**Medical Treatment** - Medication dose reduction/interruption or discontinuation, or medication initiated for event

**None** - No action is taken

### 7.3 REPORTING REQUIREMENTS

#### 7.3.1 Initial notification

If the investigator identifies a SAE, a SAE report form must be completed and sent by fax or email to Eyefree within 24 hours of the investigator's knowledge of the event. Also fax copies of hospital case reports (i.e., hospital progress notes, results of applicable diagnostic tests, lab results and biopsy results) should be sent as soon as they become available. Autopsy reports and other documents, as applicable, should be sent upon request.

Reports should be made to the following safety contact person:

[name], CEO

[contact]

Email: [contact]

The reporting should then be followed up by written notification within 5 days, using the Serious Adverse Event form in the study file.

**Any fatal or life-threatening event should be reported immediately.** These preliminary reports will be followed as soon as reasonably possible by detailed descriptions that will include a completed SAE form, copies of hospital case reports, autopsy reports, and other documents, when requested and applicable.

In accordance with European regulations, all investigators will be notified of the occurrence of serious unexpected AEs, if such AEs are associated with the use of the study device (i.e., if there is a reasonable possibility that the AE may have been caused by the device and are thus deemed significant new adverse effects or risks with respect to the investigational device).

If applicable, the investigator should also inform the representative of the appropriate local Ethics Committee, within 24 hours of investigator's awareness of the event. A copy of the report cover letter should be filed within the study file.

#### 7.3.2 Follow- Up of SADE/USADEs

Follow-up of SADEs/ USADE that occur during the study will continue until their satisfactory resolution or stabilization.

If/ when supplementary information is available, a follow-up SAE Report Form must be completed by the site and faxed within 24 hours to Eyefree Ltd.

The contact information for follow up SAE reporting is the same as for initial SAE reports (see above section).

Once faxed, the SAE form and accompanying documentation should be placed in the SAE section of the investigator's file. If supplementary information on a SAE has to be sent, the SAE form has to be used marked as 'follow-up report'.

All other SAE/AEs will be followed for new information/resolution as possible, or may be defined as 'ongoing without further follow-up' by the Investigator and Sponsor's decision.

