	
The overall duration of participation for each subject will be up to 3 weeks.
 
The place: Rambam health care campus.
 
Each subject will go through a series of 4 meetings (2 meetings per week), and up to 3 hours per meeting. Meetings will be accompanied by company representatives and/or trained study team.
 
Procedure will consist of an introduction and demonstration of the device features followed by actual use of the device by each subject (including control of gestures, use of menus, activation of pre-defined modes and writing full sentences). User feedback/questionnaire will be completed after the 2nd and 4th session.
 
The user's ability to perform each of the pre-defined tasks, will be measured in each session. In addition, success rate and measured time for completion of pre-defined tasks, collected after the 4th session, will be compared to the success rate and times collected in previous sessions.

Patient Population:	
The subject population is divided into two groups:
 
 
1. Healthy volunteers- up to 10 subjects
 
2. Early stage ALS patients – up to 5 early stage ALS patients that can still communicate orally.
 

No. of Subjects/Sites:	1 site - Rambam Health Care Campus
Study duration:	
Screening: one day.
 
Procedure: 4 sessions of about 2.5-3 hours for each participant, performed over 2 weeks' time.
 
Follow up: none.

Endpoints	
Primary endpoint:
 
Assessment of the feasibility of the use of EyeControl device, measured by:
 
 
• Ability to perform device features: 
 
○ Controlling the EyeControl's Joystick [measured by successful correct performance of over 70% of the gestures].
 
○ Controlling the Rest mode and Siren mode [measured by successful correct performance of over 70% of the gestures].
 
○ Testing the logic of the pre-defined sentences; 
 
a. ability to say 10 pre-defined sentences [over 80% success rate];
 
 
 
 
 

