## 6.2 RISKS

**1. Infra-Red Radiation:** the cameras has 4 LEDs with 850 nm wave length- and the risk is that the waves transmitted will heat the eye and by that will cause damages to the user- **This risk was tested by the SII .**

**2. Electricity damages:** the hardware of the device is composed from a battery, Odroid U3 and a speaker which can all go through an electricity damage. All the products are off the shelf products, **bearing CE mark.**

**3. Parts falling apart:** The device is not a one product device yet- so pieces of the device can be split- this risk may cause damages in a very specific conditions. – **We are creating a custom made boxes (3D printer) for the battery and the additional hardware which shouldn't be exposed.**

**4. True Emergency situations** – In cases the user truly needs to call for help and the device doesn't work. **Our pilot involves only users who can communicate without any communication device.**

**5. Allergy to the device** - In case the user has allergy to the device material (plastic, wires etc') in this case the patient will be switched.

Anticipated clinical risks to the participants, based on the above hazards may be (but not limited to); headache, nausea or dizziness caused by the multiple required eye-movements, local irritation due to allergy to device materials (glasses), burning sensation in the eyes.

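### Section 7.3.2 lets a non-serious device-related event be closed while ongoing with no stated criterion, and no contact follows meeting 4, so its duration and outcome may go unrecorded

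*Protocol*

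**What the plan says.** Protocol section 7.3.2 sets two standards of follow-up. For serious device effects it is firm: "Follow-up of SADEs/ USADE that occur during the study will continue until their satisfactory resolution or stabilization". For everything else it offers two branches: such events are followed where possible, or they "may be defined as 'ongoing without further follow-up' by the Investigator and Sponsor's decision". It gives no criterion, minimum observation time or test of relatedness for choosing the second branch.

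The synopsis, under study duration, says "Follow up: none". Section 4.5 has the study exit form completed at meeting 4, and Appendix A shows no visit after it.

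Section 7.1.3 makes an event serious if, among other criteria, it "Resulted in a permanent impairment of a body structure or a body function". Section 7.1.4 makes such an event a SADE if it is also a device effect. Section 7.2 asks for duration and outcome for each adverse event, and section 7.2.3 allows Ongoing and Unknown as outcomes. The only safety endpoint (section 1.7) is a count of device-related adverse events.

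**The concern.** The firm rule depends on how an event is classed at the time, yet the class can depend on how the event turns out. A device-related symptom that looks minor falls under the weaker rule. Whether it later proves to be a permanent impairment, and so a SADE, is known only if somebody keeps asking, and the weaker rule allows them to stop.

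The anticipated clinical risks in section 6.2 are headache, nausea, dizziness, local irritation and "burning sensation in the eyes". These would ordinarily begin as non-serious, so the weaker rule is likely to govern most of what this study sees. It is a first-in-human study whose objective includes safety. Section 2 also has safety concerns from the healthy volunteers considered before ALS patients are enrolled. A volunteer's event closed while ongoing brings less information to that step.

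**Working it through.** No stated figure needs reproducing. The check sets the passages side by side and adds up the scheduled observation time.

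**1. Which events fall under which rule.** A SADE is a device effect that meets a seriousness criterion (7.1.4). A non-serious device effect is therefore outside the compulsory rule, whatever its rated relationship to the device. The same weaker rule also covers serious events judged unrelated.

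**2. How long a device-related symptom stays under scheduled observation.** Inputs: Appendix A puts each meeting 3 ± 1 days after the previous one, so 2 to 4 days per interval. Sections 4.3 to 4.5 put meeting 2 at 2–3 days after meeting 1, meeting 3 at 7 days after meeting 1, and meeting 4 at 2–3 days after meeting 3. Time remaining is the sum of the intervals up to meeting 4.

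| Symptom starts at | Appendix A | Sections 4.3–4.5 |
|---|---|---|
| Meeting 1 | 3×2 to 3×4 = 6–12 days | 7+2 to 7+3 = 9–10 days |
| Meeting 2 | 2×2 to 2×4 = 4–8 days | (7−3)+2 to (7−2)+3 = 6–8 days |
| Meeting 3 | 2–4 days | 2–3 days |
| Meeting 4 | 0 days | 0 days |

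The two schedules differ slightly but agree in the last row. Any symptom still present at meeting 4, whenever it began, also has 0 days of scheduled observation left.

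**3. What could still reveal a lasting impairment after exit.**
- Follow-up where possible (7.3.2): this is the default, but no visit or call is scheduled to carry it out.
- Reclassification (7.1.3 and 7.1.4): permanent impairment makes the event a SADE and brings it under the compulsory rule, but only once someone learns of it.
- Medical judgement (7.1.3): an event may be classed serious in advance if it may jeopardize the subject and may need intervention to prevent a listed outcome. This covers an event that looks threatening, not one that looks mild.
- The clause on the period after the study (7.1.3): it concerns a new related serious event. It does not clearly cover the persistence of one already recorded, and it schedules no contact.
- Study completion (12.4): a statement of outcome is required for each reported SAE. Nothing equivalent is required for a non-serious device effect.

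Each route is real, but none guarantees that the course of an ongoing non-serious device effect is learned.

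**4. Effect on the endpoint.** One device-related event adds 1 to the count whether it is followed to resolution, closed as ongoing or later reclassified as serious. The change in the endpoint is 0. What changes is the recorded duration, the final outcome and possibly the seriousness class.

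**The case against.** The strongest reply is that section 7.3.2 does not abandon these events. Its default is to follow them, closure is an option shared by investigator and sponsor, and a known permanent impairment is reclassified and reported under 7.1.3, 7.1.4 and 7.3.1. Compulsory follow-up of every mild headache after four sessions of up to 3 hours could be called a preference. Most of this stands and it limits the point, but it does not supply a criterion for closing a device-related event or a contact after meeting 4.

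Several stronger readings are tempting and the documents do not support them:
- *Lasting harm would never be learned.* It may go unlearned. The default follow-up and the reclassification route can both reveal it.
- *A passing symptom and a lasting one leave the same record.* Section 7.2 records dates, duration and severity, and section 7.2.3 separates Recovered, Ongoing and Recovered with sequelae. A symptom that resolves under observation is recorded as such. The two cases merge only if the symptom is present at closure and nothing more is heard.
- *Section 7.2.3 limits SAE forms to deaths.* The note "The SAE CRF must be completed for this outcome" stands beside Death, but section 7.3.1 requires the form for any SAE that the investigator identifies.
- *The infrared hazard makes lasting eye damage the main worry.* Section 6.2 says that this risk was tested, and section 6.1.1 reports the light source as Exempt Group and the device as safe in that respect. The point does not rest on heating of the eye.

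**Conclusion.** The point holds in a limited form. Section 7.3.2 allows a non-serious device-related event to be closed while ongoing without a stated criterion. With no contact after meeting 4, the duration and final outcome of a symptom present at exit may go unrecorded, and a lasting impairment that would make it a SADE may be missed.

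The size can be stated only as observation time: 0 scheduled days for a symptom present at meeting 4, and at most 12 for one that starts at meeting 1. The documents give no event rate, so the number of affected subjects is unknown, with a ceiling of 10 + 5 = 15 enrolled. The number of device-related events is unchanged.

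Two assumptions are involved: that some device-related symptom can be present at exit, and that the anticipated symptoms usually begin as non-serious. The second is an inference, since section 6.2 gives no seriousness grade and does not claim to be complete. The change is worth making because it alters a stated rule at little cost and improves the safety information that the study exists to collect.

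**What to change.** In section 7.3.2, extend the compulsory rule now reserved for SADEs and USADEs to all adverse device effects. For example: *Every adverse device effect recorded during the study, serious or not, is followed until it has resolved or stabilized.* The option to close an event as ongoing would then remain only for events that are not device effects. Add that the seriousness of a device effect still ongoing at exit is reassessed against section 7.1.3 when its outcome is known. In the report, list the final outcome of each device-related event beside the count. The change concerns recording only and prescribes no treatment.

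The cost is the protocol wording, a few follow-up contacts by existing site staff for those of the at most 15 subjects who leave with an open device-related event, and a slightly later close-out for them.

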### **7.3.3 Notification to Authorities (CA/IECs)**

Events will be reviewed to determine any reporting obligations to Competent Authorities as well as IECs. Reporting to Competent Authorities will occur within the timelines described as per local regulations.

In the event of a USADE, sponsor or designee will conduct and report the results of an evaluation to the Competent Authorities (as appropriate), reviewing IEC, and all participating investigators within 7 working days after sponsor first receives notice of the effect, unless the USADE indicates an imminent risk of death, serious injury, or serious illness and requires prompt remedial action, in which case reporting will occur within 2 days.

## **8 DEVICE DEFICIENCY**

A Device deficiency is an inadequacy of a medical device related to its identity, quality, durability, reliability, safety or performance, such as malfunction, misuse or use error and inadequate labeling.

All investigational device deficiencies will be documented on the appropriate Device malfunction CRF and the device should be returned to the study sponsor for analysis, if possible. Instructions for returning the investigational device will be provided. Device deficiencies should also be documented in the subject's medical record.

Device deficiencies are not to be reported as AEs. However, if there is an AE that results from a device deficiency, that specific event would be recorded on the appropriate CRF.

## **9 STATISTICAL ANALYSIS PLAN**

The planned sample size is considered adequate for this study. No formal sample size calculation was performed for this study, as the study was not expected to show statistical significance or statistical power.

## **10 ETHICS AND REGULATORY**

### **10.1 INDEPENDENT ETHICS COMMITTEE (IEC) AND COMPETENT AUTHORITY (CA)**

Prior to initiation of the study, the PI will submit the study protocol and amendments, sample Informed Consent Form (ICF), and any other documents that may be requested to the IEC for review and approval. The PI/Sponsor will request that the IEC and CA (if applicable) provide written approval of the study and will keep on file records of approval of all documents pertaining to this study. The PI will not begin the study until the protocol and ICF have been approved by the IEC and CA (if applicable). The PI must agree to make any required progress reports to the IEC and CA, as well as reports of SAEs, life-threatening conditions, or death.

